8.3.3.2. Food effect

For Part 2, statistical analyses will be carried out to assess treatment (food effect) of GSK1325756 for AUC(0-t) and Cmax using Mixed effect model:

$$\log_e (Y_{ij}) = \mu + S_i + t_j + p_k + \varepsilon_{ij}$$

Y_{ij} : PK parameter (AUC(0-t), Cmax) on the j th treatment for i th subject

μ : Overall mean (Intercept)

S_i : Random effect for subject i following normal distribution $N(0, \sigma_b^2)$

t_i : Treatment effect ($j=\text{fasted, fed}$)

p_k : Period effect ($k=\text{period 1, period 2}$)

ε_{ij} : Random error following normal distribution $N(0, \sigma_w^2)$

Following loge-transformation, AUC (0-t) and Cmax will be separately analysed using a mixed effects model fitting terms for treatment and period as fixed effects, and subject as a random effect in order to assess food effect of GSK1325756 (Fed vs. Fasted). The Kenward & Roger (KR) degrees of freedom approach will be used.

Point estimates for the adjusted means on the loge scale, the mean difference between treatments and associated 90% confidence interval will be constructed using the residual variance. The point estimate and confidence interval will then be exponentially back-transformed to obtain adjusted (least square) geometric means for each treatment, and point estimates and associated 90% confidence interval for the ratio of fasted/fed.

Estimates of within-subject variability (CVw (%)) for AUC (0-t) and Cmax will also be provided. CVw (%) will be calculated based on the loge-normal distribution where:

CVw (%)= SQRT(exp(MSE)-1) * 100. (MSE is the residual mean squared error from the model)

10. APPENDICES

Section	Appendix
RAP Section 4 : Analysis Populations	
Section 10.1	Appendix 1: Protocol Deviation Management
RAP Section 5 : General Considerations for Data Analyses & Data Handling Conventions	
Section 10.2	Appendix 2: Time and Events
Section 10.3	Appendix 3: Treatment States & Phases
Section 10.4	Appendix 4: Data Display Standards & Handling Conventions 
 • Study Treatment • Baseline Definitions & Derivations • Reporting Process & Standards
Section 10.5	Appendix 5: Derived and Transformed Data 
 • General • Study Population • Safety • Pharmacokinetics
Section 10.6	Appendix 6: Premature Withdrawals & Handling of Missing Data 
 • General • Study Population & Safety
Section 10.7	Appendix 7: Values of Potential Clinical Importance 
 • Laboratory Values • ECG • Vital Signs
Other RAP Appendices	
Section 10.8	Appendix 8: Abbreviations & Trade Marks
Section 10.9	Appendix 9: List of Data Displays
Section 10.10	Appendix 10: Example Mock Shells for Data Displays

10.1. Appendix 1: Protocol Deviation Management

Details will be referred latest Protocol Deviation Management Plan and data handling will be decided prior to final data base release.

10.2. Appendix 2: Time & Events

Part 1, Period 1-2

Day	Screening	Day-1	Day 1												Day 2	Day 3	
Time post-dose			Pre-dose	0 h	0.25 h	0.5 h	0.75 h	1 h	2 h	3 h	4 h	6 h	8 h	10 h	12 h	24 h	48 h
Informed consent	X																
Subject demography /Medical history	X																
Height, Weight, BMI	X																
Urine drug screen	X																
Serological test	X																
Physical examination	X	X	X									X				X	X
Vital signs (PR, BP, temp)	X	X	X									X				X	X
12-lead ECG	X	X	X									X				X	X
Ophthalmic examination	X ³																
SAEs ²	<=====>																
AEs ²	<=====>																
Con Med review	<=====>																
Hematology, clinical chemistry and urinalysis	X	X															X
Administration				X													
PK sampling			X		X	X	X	X	X	X	X	X	X	X	X	X	
Admission			X														
Discharge																	X

1. Screening visit will occur only prior to the first dosing. Treatment Period 2 will occur after at least 7-days wash-out period. High fat meal will be started and completed before within 30 minutes of GSK1325756H/Placebo dosing.
2. All SAEs will be collected from the signing of the ICF until the follow-up visit at the time points specified. All AEs will be collected from the start of treatment until the follow-up visit at the time points specified (see Section 9.1 Adverse Events).
3. Ophthalmic examinations are conducted on the day between Screening and Day-1. However, it is not carried out for those who are ineligible due to other screening criteria.

Part 1, Period 3

Day	Day-1	Day 1												Day 2	Day 3	Day 4	Follow up ^{2,3}		
		Pre-dose	0 h	0.25 h	0.5 h	0.75 h	1 h	2 h	3 h	4 h	6 h	8 h	10 h	12 h	24 h	48 h	60 h	72 h	
Physical examination	X	X								X					X	X		X	X
Vital signs (PR, BP, temp)	X	X								X					X	X		X	X
12-lead ECG	X	X								X					X	X		X	X
Ophthalmic examination																			X
SAEs	<=====>																		
AEs	<=====>																		
Con Med review	<=====>																		
Hematology, clinical chemistry and urinalysis	X																	X	X
Administration			X																
PK sampling		X		X	X	X	X	X	X	X	X	X	X	X	X	X	X	X	
Admission	X																		
Discharge																			X

1. Treatment Period 3 will occur after at least 7-days wash-out period. High fat meal will be started and completed before within 30 minutes of GSK1325756/Placebo dosing.
2. Follow up visit will occur after 7 days (+/- 1day) of the last dosing.
3. In the case where the subject has discontinued the study prematurely, the assessments for follow up will be carried out.

Part 2, Period 1-2

Day	Screening	Day-1	Day 1												Day 2	Day 3	Follow up ^{3,5}	
			Pre-dose	0 h	0.25 h	0.5 h	0.75 h	1 h	2 h	3 h	4 h	6 h	8 h	10 h	12 h	24 h	48 h	
Informed consent	X																	
Subject demography /Medical history	X																	
Height, Weight, BMI	X																	
Urine drug screen	X																	
Serological test	X																	
Physical examination	X	X	X									X			X	X	X	
Vital signs (PR, BP, temp)	X	X	X									X			X	X	X	
12-lead ECG	X	X	X									X			X	X	X	
Ophthalmic examination		X ⁶															X	
SAEs ⁴	<=====>															<=====>		
AEs ⁴	<=====>															<=====>		
Con Med review	<=====>															<=====>		
Hematology, clinical chemistry and urinalysis	X	X															X	X
Administration				X														
PK sampling			X		X	X	X	X	X	X	X	X	X	X	X	X		
Admission		X																
Discharge																	X	

1. Screening visit will occur only prior to the first dosing. Treatment Period 2 will occur after at least 7-days wash-out period.
2. For the fed condition, meal will be started and completed before within 30 minutes of GSK1325756H dosing.
3. Follow up visit will occur after 7-days (+/- 1 day) of the last dosing.
4. All SAEs will be collected from the signing of the ICF until the follow-up visit at the time points specified. All AEs will be collected from the start of treatment until the follow-up visit at the time points specified (see Section 9.1 Adverse Events).
5. In the case where the subject has discontinued the study prematurely, the assessments for follow up will be carried out.
6. Ophthalmic examinations are conducted on the day between Screening and Day-1. However, it is not carried out for those who are ineligible due to other screening criteria.

10.3. Appendix 3: Treatment States and Phases

10.3.1. Treatment Phases

Assessments and events will be classified according to the time of occurrence relative to the assessment date.

Treatment Phase	Definition
Part 1: Period 1	Assessment Date < Previous Day of Dosing Start Date in Period 2 (Part 1)
Part 1: Period 2	Previous Day of Dosing Start Date in Period 2 ≤ Assessment Date < Previous Day of Dosing Start Date in Period 3 (Part 1)
Part 1: Period 3	Previous Day of Dosing Start Date in Period 3 ≤ Assessment Date (Part 1)
Part 2: Period 1	Assessment Date < Previous Day of Dosing Start Date in Period 2 (Part 2)
Part 2: Period 2	Previous Day of Dosing Start Date in Period 2 ≤ Assessment Date (Part 2)

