7. SAFETY ANALYSES

The safety analyses will be based on the Safety Population, unless otherwise specified. These analyses will be performed in each part.

Adverse events occurred in washout period will be included in adverse events analyses for previous period. Also adverse events occurred in follow up period will be included in safety analyses for the last period.

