10.3.2.1. Treatment States for AE Data

Treatment State	Definition
Pre-Treatment	AE Start Date and Time < Dosing Start Date and Time
Part 1: Period 1	Dosing Start Date and Time in Period 1 ≤ AE Start Date and Time < Dosing Start Date and Time in Period 2 (Part 1)
Part 1: Period 2	Dosing Start Date and Time in Period 2 ≤ AE Start Date and Time < Dosing Start Date and Time in Period 3 (Part 1)
Part 1: Period 3	Dosing Start Date and Time in Period 3 ≤ AE Start Date and Time (Part 1)
Part 2: Period 1	Dosing Start Date and Time in Period 1 ≤ AE Start Date and Time < Dosing Start Date and Time in Period 2 (Part 2)
Part 2: Period 2	Dosing Start Date and Time in Period 2 ≤ AE Start Date and Time (Part 2)
Onset Time Since First Dose (Minute)	If Dosing Start Date and Time > AE Onset Date and Time = AE Onset Date and Time – Dosing Start Date and Time If dosing Start Date and Time ≤ AE Onset Date and Time = AE Onset Date and Time - Dosing Start Date and Time +1 Missing otherwise
Onset Time Since Last Dose (Minute)	AE Start Date and Time – Most Recent Treatment Start Date and Time + 1
Duration (Minute)	AE Resolution Date and Time – AE Onset Date and Time + 1
Drug-related	If relationship is marked 'YES' on eCRF

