10.4.2. Sequence group Display Descriptors

Sequence Group Descriptions			
RandAll NG		Data Displays for Reporting	
Code	Description	Description [1]	Order
A	X1/X2/P	A	1
B	X1/P/X3	B	2
C	P/X2/X3	C	3
D	X2/X4	D	4
E	X4/X2	E	5

NOTES:

1. Footnote will be added in displays as follows.
A: 10mg (Fed) / 50mg (Fed) / Placebo (Fed), B: 10mg (Fed) / Placebo (Fed) / 100mg (Fed), C: Placebo (Fed) / 50mg (Fed) / 100mg (Fed), D: 50mg (Fed) / 50mg (Fasted) , E: 50mg (Fasted) / 50mg (Fed)

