10.4.3. Baseline Definition & Derivations

10.4.3.1. Baseline Definitions

Parameter	Study Assessments Considered as Baseline			Baseline Used in Data Display
	Screening	Day -1	Day 1 (Pre-Dose)	
Safety				
12 Lead ECG & Vital Signs	X	X	X	Day 1 (Pre Dose)
Haematology	X	X		Day -1
Clinical Chemistry	X	X		Day -1

NOTES:

- The baseline will be defined for each period in Part 1 and Part 2.

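### In Part 1, end-of-washout tests count only towards the next treatment, so post-baseline safety summaries follow 10 mg and 50 mg to 48 h but 100 mg to about one week

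*SAP*

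**What the plan says.** SAP 10.3.1 sorts assessments by date. Part 1 Period 1 takes results with "Assessment Date < Previous Day of Dosing Start Date in Period 2 (Part 1", Period 2 takes those with "Previous Day of Dosing Start Date in Period 2 ≤ Assessment Date < Previous Day of Dosing Start Date in Period 3 (Part 1", and Period 3 takes the rest. The day before a dose therefore opens the new period.

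Adverse events are cut at a different point. SAP 10.3.2.1 keeps an event in Period 1 as long as "AE Start Date and Time < Dosing Start Date and Time in Period 2 (Part 1", and SAP 7 says "Adverse events occurred in washout period will be included in adverse events analyses for previous period".

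On baselines, SAP 10.4.3.1 says "The baseline will be defined for each period in Part 1 and Part 2". It uses Day -1 for haematology and chemistry, and Day 1 pre-dose for ECG and vital signs.

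The Part 1 sequences in SAP 10.4.2 are "A: 10mg (Fed) / 50mg (Fed) / Placebo (Fed), B: 10mg (Fed) / Placebo (Fed) / 100mg (Fed" and "C: Placebo (Fed) / 50mg (Fed) / 100mg (Fed".

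In the time and events tables (Protocol 2, SAP 10.2), the last in-unit tests in Part 1 Periods 1 and 2 are at 48 h, and in Period 3 at 72 h. The only follow-up visit comes 7 days (±1) after the last dose. SAP 10.5.1 provides for an any-visit post-baseline row in the safety summaries. The LB4 shell has a worst-case post-baseline row and the EG1 shell an any-time row.

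**The concern.** The end-of-washout visit is the only scheduled look at a participant between 48 h and the next dose. Its measurements are filed under the next treatment, while an adverse event first noted there is filed under the previous one. Take Sequence B with a raised ALT on Day -1 of Period 2. The value is shown under placebo and becomes placebo's baseline. If the investigator also records it as an adverse event, that event counts under 10 mg. The 10 mg laboratory tables show no sign of it.

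The larger consequence concerns the comparison between doses. Each active dose in Part 1 is given in one period only, and only the 100 mg period has follow-up. A row that asks whether a participant was ever abnormal after baseline therefore looks longer and more often at 100 mg than at 10 or 50 mg. Neutrophil reduction is a named risk in Protocol 3.3.1, monitored through this same schedule, so the haematology tables are among those affected.

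**Working it through.** The plan gives no figure for this point, so the check is a count under its own rules. The sequences give 12 participants per active dose, which agrees with Protocol 10.1.1.

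**Inputs.** Six participants per sequence (SAP 2.3); sequences from SAP 10.4.2; period boundaries from SAP 10.3.1; test times from SAP 10.2. In Periods 1 and 2 the counted post-dose tests are one laboratory draw (48 h) and three ECGs (one on Day 1, then 24 h and 48 h). In Period 3 they are two laboratory draws (72 h, follow-up) and five ECGs (one on Day 1, then 24 h, 48 h, 72 h and follow-up).

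**Part 1 count, continuing participants.**

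| Treatment | Sequence and period | Participant-periods | With a counted test after 48 h | Laboratory draws each | ECGs each |
|---|---|---|---|---|---|
| 10 mg | A1, B1 | 12 | 0 | 1 | 3 |
| 50 mg | A2, C2 | 12 | 0 | 1 | 3 |
| 100 mg | B3, C3 | 12 | 12 | 2 | 5 |
| Placebo | C1, B2, A3 | 18 | 6 (A3 only) | 1, 1, 2 | 3, 3, 5 |

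In total, 12 + 6 = 18 of 54 participant-periods have a counted late test and 36 do not.

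**Part 2 count.** The sequences are "D: 50mg (Fed) / 50mg (Fasted) , E: 50mg (Fasted) / 50mg (Fed", with eight participants each and follow-up after Period 2 only. Fed has 8 of 16 doses with a counted late test (E2) and fasted 8 of 16 (D2). That is 16 of 32 without one, equally split. Over both parts, 50 mg has 16 of 12 + 32 = 44 doses with a counted late test.

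**Are the missing tests actually done?** Yes. At the minimum 7-day interval, Day -1 falls (7 − 1) × 24 = 144 h after the previous dose and the pre-dose tests about 168 h after it. The follow-up window of 7 ± 1 days is 144 to 192 h. If the end-of-washout tests were also credited to the preceding dose, the Part 1 counts would be 12/12, 12/12, 12/12 and 18/18.

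**Illustration of the effect.** Assume a chance *p* that any one result is out of range with no drug effect. With *k* independent results, the chance of at least one is 1 − (1 − *p*)^*k*. The documents give no *p*, so two values are shown.

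| *p* | Laboratory, k = 1 (10, 50 mg) | Laboratory, k = 2 (100 mg) | ECG, k = 3 (10, 50 mg) | ECG, k = 5 (100 mg) |
|---|---|---|---|---|
| 2% | 2.0% | 3.96% | 5.9% | 9.6% |
| 5% | 5.0% | 9.75% | 14.3% | 22.6% |

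Independence is the extreme case here. If a participant's results were perfectly correlated, the columns would not differ. At *p* = 5% the laboratory rate at 100 mg therefore lies between 5.0% and 9.75% for non-negative correlation. Among 12 participants that is 0.6 to about 1.2 per test, against 0.6 at the lower doses.

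**The case against.** The strongest reply is that this is by design. Protocol 5.4 cites a half-life of about 11 to 12 h, judges three days enough for PK and safety in Periods 1 and 2, and regards seven days as adequate washout. At 144 h about 12 half-lives have passed (144 / 12), so treating that visit as a fresh baseline is reasonable. Different rules for events and measurements are also not contradictory in themselves: an event that begins before a dose cannot be due to that dose, while a pre-dose measurement is needed as a baseline. Both arguments stand as reasons to keep the period baselines. Neither removes the imbalance in rows that pool all post-baseline visits, because 100 mg is still credited with tests that the lower doses are not.

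A reader might infer more than the documents support:

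- **That 50 mg has no counted late test anywhere.** Part 2 has one after 16 of its 32 doses. It does not repair the Part 1 tables, which are produced separately, and Part 2 uses a different meal.
- **That fed and fasted are compared unfairly.** The Part 2 gap follows period and is balanced between the two conditions.
- **That late findings are lost.** Adverse events are tabulated under the previous treatment. All values are listed by participant, with separate listings for anyone with a value of potential clinical importance. Unscheduled results are listed, though not summarised, and early leavers receive the follow-up tests.
- **That every abnormality appears under two treatments.** This happens only if the investigator reports it as an adverse event.
- **That a false dose trend will appear.** The rates above are assumptions, the groups are small, safety is descriptive with no formal comparison, and by-time rows are not affected by the number of visits.

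**Conclusion.** The point holds for Part 1 as a defect in how safety results are allocated and pooled. Followed as written, the SAP counts scheduled tests after 48 h for 0/12 at 10 mg, 0/12 at 50 mg, 6/18 on placebo and 12/12 at 100 mg. Any-visit and worst-case rows compare one, one and two laboratory draws, and three, three and five ECGs. The counts follow from the documents for participants who continue, and need no outside assumption. The size of the distortion does: it can range from nothing to nearly double for a laboratory test, depending on the abnormality rate and on how strongly one person's results agree. Part 2 merits a parallel note only. The change is worth making because the data that would even out the comparison are already collected.

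**What to change.** Leave the baselines in SAP 10.4.3.1 as they are: Day -1 for laboratory tests, Day 1 pre-dose for ECG and vital signs. Then amend SAP 10.3.1 and the display rules as follows.

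1. Also show the end-of-washout result as a labelled post-dose time point for the preceding treatment, as change from that treatment's own baseline. For ECG and vital signs, name in advance which of the Day -1 and pre-dose readings is used, so that each dose contributes one. Give the actual days since dose, because the washout has a minimum but no maximum.
2. Build any-visit and worst-case rows from comparable time points at every dose. For laboratory tests, use in-unit discharge plus end-of-washout or follow-up. For ECG and vital signs, use the Day 1 post-dose, 24 h and 48 h readings plus end-of-washout or follow-up. Keep the Period 3 72 h ECG and vital signs in the by-time rows.
3. State in SAP 7 how this time point relates to the adverse-event cut at the dosing time.
4. Apply the same display in Part 2 for consistency.

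This needs SAP wording, one derived visit and a footnote, with no new data. The drawbacks are that one result appears under two treatments, which the footnote must explain, and that the end-of-washout interval varies between participants and so matches the follow-up visit only approximately.

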10.3.2. Treatment States

Assessments and events will be classified according to time of occurrence relative to the start and/or stop date of the study treatment.

10.3.2.1. Treatment States for AE Data

Treatment State	Definition
Pre-Treatment	AE Start Date and Time < Dosing Start Date and Time
Part 1: Period 1	Dosing Start Date and Time in Period 1 ≤ AE Start Date and Time < Dosing Start Date and Time in Period 2 (Part 1)
Part 1: Period 2	Dosing Start Date and Time in Period 2 ≤ AE Start Date and Time < Dosing Start Date and Time in Period 3 (Part 1)
Part 1: Period 3	Dosing Start Date and Time in Period 3 ≤ AE Start Date and Time (Part 1)
Part 2: Period 1	Dosing Start Date and Time in Period 1 ≤ AE Start Date and Time < Dosing Start Date and Time in Period 2 (Part 2)
Part 2: Period 2	Dosing Start Date and Time in Period 2 ≤ AE Start Date and Time (Part 2)
Onset Time Since First Dose (Minute)	If Dosing Start Date and Time > AE Onset Date and Time = AE Onset Date and Time – Dosing Start Date and Time If dosing Start Date and Time ≤ AE Onset Date and Time = AE Onset Date and Time - Dosing Start Date and Time +1 Missing otherwise
Onset Time Since Last Dose (Minute)	AE Start Date and Time – Most Recent Treatment Start Date and Time + 1
Duration (Minute)	AE Resolution Date and Time – AE Onset Date and Time + 1
Drug-related	If relationship is marked 'YES' on eCRF

10.4. Appendix 4: Data Display Standards & Handling Conventions

10.4.1. Study Treatment & Sub-group Display Descriptors

Treatment Group Descriptions			
Part1 (Schedule1)			
RandAll NG		Data Displays for Reporting	
Code	Description	Description	Order [1]
P	Placebo, Fed	Placebo, Fed	1
X1	GSK1325756H 10 mg, Fed	GSK1325756H 10 mg, Fed	2
X2	GSK1325756H 50 mg, Fed	GSK1325756H 50 mg, Fed	3
X3	GSK1325756H 100 mg, Fed	GSK1325756H 100 mg, Fed	4
Part2 (Schedule2)			
X2	GSK1325756H 50 mg, Fed	GSK1325756H 50 mg, Fed	1
X4	GSK1325756H 50 mg, Fasted	GSK1325756H 50 mg, Fasted	2

NOTES:

1. Order in which treatments are to be presented in Listings. Note that the order in which treatments are to be presented in Tables, active treatment (X1, X2, X3 in Part 1, X2, X4 in Part 2) is shown in the first and placebo (P in Part 1) in the second.

10.4.2. Sequence group Display Descriptors

Sequence Group Descriptions			
RandAll NG		Data Displays for Reporting	
Code	Description	Description [1]	Order
A	X1/X2/P	A	1
B	X1/P/X3	B	2
C	P/X2/X3	C	3
D	X2/X4	D	4
E	X4/X2	E	5

NOTES:

1. Footnote will be added in displays as follows.
A: 10mg (Fed) / 50mg (Fed) / Placebo (Fed), B: 10mg (Fed) / Placebo (Fed) / 100mg (Fed), C: Placebo (Fed) / 50mg (Fed) / 100mg (Fed), D: 50mg (Fed) / 50mg (Fasted) , E: 50mg (Fasted) / 50mg (Fed)

10.4.3. Baseline Definition & Derivations

10.4.3.1. Baseline Definitions

Parameter	Study Assessments Considered as Baseline			Baseline Used in Data Display
	Screening	Day -1	Day 1 (Pre-Dose)	
Safety				
12 Lead ECG & Vital Signs	X	X	X	Day 1 (Pre Dose)
Haematology	X	X		Day -1
Clinical Chemistry	X	X		Day -1

NOTES:

- The baseline will be defined for each period in Part 1 and Part 2.

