9. STUDY ASSESSMENTS AND PROCEDURES

- Study procedures and their timing are summarized in the SoA.
- Protocol waivers or exemptions are not allowed

- Immediate safety concerns should be discussed with the sponsor immediately upon occurrence or awareness to determine if the participant should continue or discontinue study treatment.
- Adherence to the study design requirements, including those specified in the SoA, is essential and required for study conduct.
- All screening evaluations must be completed and reviewed to confirm that potential participants meet all eligibility criteria. The investigator will maintain a screening log to record details of all participants screened and to confirm eligibility or record reasons for screening failure, as applicable.
- Procedures conducted as part of the participant's routine clinical management (e.g., blood count) and obtained before signing of ICF may be utilized for screening or baseline purposes provided the procedure met the protocol-specified criteria and was performed within the time frame defined in the SoA.
 - The maximum amount of blood collected from each participant over the duration of the study, including any extra assessments that may be required, will not exceed 400 mL.
 - Repeat or unscheduled samples may be taken for safety reasons or for technical issues with the samples.

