Dosing	
Part 1:
 
Subjects will have a screening visit within 30 days prior to the first dose of study. A minimum washout period of 7 days will be required between each treatment period. Subjects will receive three treatment periods in the study. Subjects will be housed in the Clinical Research Unit from Day -1 (the day before dosing) through Day 3 for Period 1 and 2, and from Day -1 (the day before dosing) through Day 4 for Period 3. Subjects will return to the clinic 7 days (at least) after the previous administration day for Period 1 and 2, and subjects will visit the unit on Day 8 (+/- 1 day) of the last dosing for Period 3 for follow-up.
 
Part 2:
 
Subjects will have a screening visit within 30 days prior to the first dose of study treatment, two treatment periods separated by at least 7 days, and follow-up. Subjects will be housed in the Clinical Research Unit from Day -1 (the day before dosing) through Day 3 (for Period 1 and 2), and re-visit 7 (± 1) days after the last dose of Period 2 for follow-up.
																													

Overview of Study Design and Key Features	

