10.4.3.2. Derivations and Handling of Missing Baseline Data

Definition	Reporting Details
Change from Baseline	= Post-Dose Visit Value – Baseline

NOTES:

- Unless otherwise specified, the baseline definitions specified in Section 10.4.3.1 Baseline Definitions will be used for derivations for endpoints / parameters and indicated on summaries and listings.
- Unless otherwise stated, if baseline data is missing no derivation will be performed and will be set to missing.
- The baseline definition will be footnoted on all change from baseline displays.

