10.9.5. Safety Tables

Safety: Tables					
No.	Population	IDSL / TST ID / Example Shell	Title	Programming Notes	Deliverable [Priority]
Adverse Events (AEs)					
2.1.	Safety	AE1	Summary of All Adverse Events by System Organ Class and Preferred Term (Part 1)		PR [1]
2.2.	Safety	AE5A	Summary of All Adverse Events by Maximum Intensity (Part 1)		PR [1]
2.3.	Safety	AE1	Summary All Drug-Related Adverse Events by System Organ Class and Preferred Term (Part 1)		PR [1]
2.4.	Safety	AE5A	Summary All Drug-Related Adverse Events by Maximum Intensity (Part 1)		PR [1]
2.5.	Safety	AE1	Summary of All Adverse Events by System Organ Class and Preferred Term (Part 2)		SAC [2]
2.6.	Safety	AE5A	Summary of All Adverse Events by Maximum Intensity (Part 2)		SAC [2]
2.7.	Safety	AE1	Summary All Drug-Related Adverse Events by System Organ Class and Preferred Term (Part 2)		SAC [2]
2.8.	Safety	AE5A	Summary All Drug-Related Adverse Events by Maximum Intensity (Part 2)		SAC [2]
Laboratory: Chemistry					
2.9.	Safety	LB1	Summary of Chemistry (Part 1)		PR [1]
2.10.	Safety	LB1	Summary of Chemistry Changes from Baseline (Part 1)		PR [1]
2.11.	Safety	LB4	Summary of Chemistry Data Shifts from Baseline with Respect to the Normal Range (Part 1)		PR [1]
2.12.	Safety	LB1	Summary of Chemistry (Part 2)		SAC [2]
2.13.	Safety	LB1	Summary of Chemistry Changes from Baseline (Part 2)		SAC [2]

Safety: Tables					
No.	Population	IDSL / TST ID / Example Shell	Title	Programming Notes	Deliverable [Priority]
2.14.	Safety	LB4	Summary of Chemistry Data Shifts from Baseline with Respect to the Normal Range (Part 2)		SAC [2]
Laboratory: Hematology					
2.15.	Safety	LB1	Summary of Hematology (Part 1)		PR [1]
2.16.	Safety	LB1	Summary of Hematology Changes from Baseline (Part 1)		PR [1]
2.17.	Safety	LB4	Summary of Hematology Data Shifts from Baseline with Respect to the Normal Range (Part 1)		PR [1]
2.18.	Safety	LB1	Summary of Hematology (Part 2)		SAC [2]
2.19.	Safety	LB1	Summary of Hematology Changes from Baseline (Part 2)		SAC [2]
2.20.	Safety	LB4	Summary of Hematology Data Shifts from Baseline with Respect to the Normal Range (Part 2)		SAC [2]
Laboratory: Urinalysis					
2.21.	Safety	UR3b	Summary of Urinalysis Data (Glucose, Protein, Blood, Ketones, Bilirubin, Urobilinogen) (Part 1)		PR [1]
2.22.	Safety	LB1	Summary of Urinalysis Data (Specific Gravity and pH) (Part 1)		PR [1]
2.23.	Safety	UR3b	Summary of Urinalysis Data (Glucose, Protein, Blood, Ketones, Bilirubin, Urobilinogen) (Part 2)		SAC [2]

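### Low haemoglobin, low haematocrit and high creatinine have change-only PCI limits measured from each period's Day -1, so a change that builds up across periods or arises in washout can miss the PCI flag

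*SAP*

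**What the plan says.** - **Which value is baseline.** In SAP 10.4.3.1, the column headed "Baseline Used in Data Display" gives Day -1 for haematology and clinical chemistry. The note below the table reads: "The baseline will be defined for each period in Part 1 and Part 2".
- **How far the rule reaches.** SAP 10.4.3.2: "Unless otherwise specified, the baseline definitions specified in Section 10.4.3.1 Baseline Definitions will be used for derivations for endpoints / parameters". It covers summaries and listings too, and no laboratory exception is given.
- **The limits.** SAP 10.7.1 flags low haemoglobin, low haematocrit and high creatinine only by change from baseline: a fall of 25 g/L, a fall of 0.075 and a rise of 44.2 µmol/L. There is no absolute low limit for the first two and no absolute high limit for the third. Neutrophils, platelets, white cells and electrolytes have absolute limits.
- **Period assignment.** SAP 10.3.1 starts Periods 2 and 3 on the day before dosing and leaves the last period open-ended. A later Day -1 value therefore belongs to the later period, and follow-up belongs to the last one.
- **Sampling.** For Part 1 the SAP states: "Subjects will receive three treatment periods in the study". Part 2 has two. In the schedule of activities, safety laboratory tests in Part 1 Periods 1 and 2 fall on Day -1 and Day 3. Period 3 has Day -1, Day 4 and follow-up. Between periods, "A minimum washout period of 7 days will be required between each treatment period".

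Sections 10.4.3, 10.7.1 and 10.3.1 read the same in the original SAP and in Amendment 1. Listing numbers below are those of Amendment 1.

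**The concern.** A within-period baseline is the natural reference for comparing treatments in a crossover. Here it is also the only reference for three safety flags that have no absolute limit behind them. From Period 2 on, the reference is a value taken after earlier dosing and blood sampling, so any shift that has already happened is absorbed into it.

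The PCI listings (38 and 39 for chemistry, 42 and 43 for haematology) are where the plan isolates participants with notable laboratory changes. A participant whose haemoglobin at follow-up is more than 25 g/L below the value before the first dose need not appear there. No planned display derives that difference. The participants are elderly and are sampled repeatedly, so a cumulative fall in haemoglobin is a reasonable thing to want to see.

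**Working it through.** The plan states no figure to reproduce. The check applies its own rule to example paths.

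**1. What the rule tests.** Let B_k be the Day -1 value of period k, E_k the last value assigned to period k, K the number of periods and T the limit. The total change from the pre-study value is

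E_K − B_1 = Σ(E_k − B_k) + Σ(B_k − E_(k−1)),

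where the second sum runs over k ≥ 2. The SAP compares changes from B_k within a period, the terms of the first sum, with T one at a time. It never compares a washout term in the second sum, or the total, with T.

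**2. Ceiling with no washout change (K × T).**

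| Parameter | T | Part 1, 3 periods | Part 2, 2 periods |
|---|---|---|---|
| Haemoglobin, g/L | 25 | 75 | 50 |
| Haematocrit | 0.075 | 0.225 | 0.15 |
| Creatinine, µmol/L | 44.2 | 132.6 | 88.4 |

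Washout change in the same direction adds to these.

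**3. Illustrative Part 1 paths.** None raises a PCI flag under the SAP. Each crosses the limit from Period 2 if measured from Period 1 Day -1.

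| Path | Change from own Day -1 | Change from Period 1 Day -1 |
|---|---|---|
| Haemoglobin 150→135→120→105 | −15, −15, −15 | −15, −30, −45 |
| Haematocrit 0.45→0.41→0.37→0.33 | −0.04, −0.04, −0.04 | −0.04, −0.08, −0.12 |
| Creatinine 70→95→120→145 | +25, +25, +25 | +25, +50, +75 |
| Haemoglobin 150→140, 125→120, 110→105 (with washout falls) | −10, −5, −5 | −10, −30, −45 |

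One washout interval can be enough. Take haemoglobin 150 on Period 1 Day -1, 148 on Day 3 and 120 on Period 2 Day -1. The Day 3 change is −2. The fall to 120 is 150 − 120 = 30 g/L, over the limit, but 120 becomes the new baseline and is compared with nothing.

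**4. How much of this also escapes the normal-range flag.** The documents give no normal ranges, so the male ranges here are assumptions: haemoglobin 130–170, 137–168 or 135–175 g/L; haematocrit 0.40–0.50, 0.407–0.501 or 0.39–0.52; creatinine 57–95, 60–110 or 53–97 µmol/L. Every path in the table above ends outside all of its assumed ranges and would be marked. A change escapes both flags only if its total exceeds T while each value stays in range, so the range width caps it:

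- haemoglobin: width 31 to 40 g/L, so up to 31/25 = 1.24 to 40/25 = 1.6 times the limit;
- haematocrit: width 0.094 to 0.13, so up to 0.094/0.075 = 1.25 to 0.13/0.075 = 1.73 times;
- creatinine: width 38 to 50 µmol/L, so 38/44.2 = 0.86 to 50/44.2 = 1.13 times, possible only at the wide end.

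Example: haemoglobin 170→160→150→140 inside 135–175 g/L. Each period shows −10 and the total is −30, with no PCI flag and no normal-range flag.

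**5. Would an added flag fire merely from sampling?** Protocol Section 9 says that blood collection "will not exceed 400 mL" per participant over the study. Assume blood volume V of 4,000 to 5,000 mL, haemoglobin of 135 to 145 g/L and replacement of volume but not cells. The fall is Hb × (1 − exp(−400/V)):

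- smallest: 135 × (1 − exp(−0.08)) = 10.4 g/L;
- largest: 145 × (1 − exp(−0.10)) = 13.8 g/L.

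Both are below 25 g/L, even at the cap.

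**The case against.** A reader might infer that a stepwise change is never flagged at all. The documents do not support that. The laboratory listing shell (CP_LB6) prints the normal range and an NR flag beside the clinical-importance flag, and all values from all periods are listed (Listings 36, 37, 40 and 41). Tables 2.11, 2.14, 2.17 and 2.20 are shift tables against the normal range. Protocol 9.3.5 requires the investigator to review each report and record clinically relevant changes during the study, with no tie to the period baseline. Laboratory values are also reviewed before each next period (Protocol 5.1), and haematocrit must be normal at screening (Protocol 6.1).

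Nor can one say that the sponsor's limit relative to the pre-study value is breached unnoticed: the limits are set against the period baseline, and none against the pre-study value exists.

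The mechanism is also weak. Doses are single, the half-life is about 11 to 12 hours (Protocol 5.4), and a 7-day washout is 168/12 = 14 half-lives or more. Each Part 1 participant has one placebo period, so three equal steps are not a drug pattern. Safety is summarised descriptively.

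All of this stands as a limit on size, but it does not close the gap. NR marks a level, not a change. Entry criteria name haematocrit and neutrophils; other out-of-range values may be accepted, and for such a participant NR is set from the start and cannot show worsening. The shift tables use the same per-period baseline, so a participant already low by a later Day -1 is counted as low-to-low. Comparing listings by eye is possible, but it is not a prespecified derivation.

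**Conclusion.** The point holds in limited form. After Period 1, no derived comparison uses the value before first dosing. For three parameters with change-only limits, a cumulative or washout-interval change beyond the limit can therefore miss the PCI flag and the PCI listings.

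The changes left without useful marking are those over the limit but inside the normal range, and those in participants already out of range or already shifted by a later Day -1. Under the assumed ranges the within-range gap is real for haemoglobin and haematocrit and marginal for creatinine. The three-fold ceiling describes the PCI flag alone, not what a reader of the full listings would miss.

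Practical weight is modest. This is a minor gap in safety reporting. It does not touch the PK analyses, and the stopping criteria in Protocol 8.1 (liver chemistry, QTc, neutrophils) do not use these flags. The per-period baseline itself is not an error.

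**What to change.** Keep the per-period baseline for all treatment summaries and shift tables. In SAP 10.4.3, for haemoglobin, haematocrit and creatinine only, add a second derived variable: change from study baseline, defined as Period 1 Day -1 of the participant's part. Derive it for every later value, including later Day -1 values and follow-up. Set the PCI flag if either change crosses the existing SAP 10.7.1 limit, and footnote in Listings 38, 39, 42 and 43 which baseline triggered it.

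The cost is one derived variable and a footnote in existing listings, with no new samples and no new limits. The downside is that a flag triggered by the study baseline cannot be attributed to a single treatment and may fall in a placebo period, which the footnote should make clear.
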